4.5. Administration of Study Medication

In the main trial, IVX-A12 +/- MF59 or placebo will be administered intramuscularly as a single dose.

4.6. Trial Procedures

4.6.1. Main Trial Procedures

Randomization will occur simultaneously into all three vaccine trial groups (IVX-A12a, IVX-A12d, and placebo). Initial vaccinations will be performed in sentinel subjects and then expanded to the remaining subjects in each of the three trial groups. In total, there will be 40 sentinels. In each IVX-A12 group, 16 sentinel subjects will receive IVX-A12a (8 subjects from age stratum 60 to 69 years of age and 8 subjects from age stratum 70 to 85 years age); 16 sentinel subjects will receive IVX-A12d (8 subjects from age stratum 60 to 69 years of age and 8 subjects from age stratum 70 to 85 years age). In the placebo group, 8 sentinel subjects will receive placebo (4 subjects from age stratum 60 to 69 years of age and 4 subjects from age stratum 70 to 85 years of age). Sentinels will be closely monitored for a minimum of 48 hours. If no stopping rules are triggered, the remaining subjects in the IVX-A12 and placebo groups will be enrolled. The independent SMC will be responsible for the application of stopping rules, if achieved.

Trial subjects will receive a single dose on Day 0 (Study Day 1). The cohorts are shown in [Table 1](#). The Time and Events Schedule is described in the protocol.

There will be a total of seven scheduled clinic visits required for each subject (at screening, then Days 0, 7, 28, 90, 180, and 365), and five phone contacts (on Days 3, 14, 56, 135, and 270) for all subjects.

4.6.2. Observational Extension Trial Procedures

There will be a total of two scheduled clinic visits required for each subject (Day 365 and Day 730) and one phone contact (on Day 545) for all subjects. Note: The Sponsor terminated the trial prior to Day 545.

This document is confidential.

5. Endpoints

The primary, secondary, and exploratory endpoints used to evaluate safety and immunogenicity are described in the following sections:

5.1. Main Trial Endpoints

5.1.1. Primary Endpoint(s)

5.1.1.1. Co-primary Endpoints (Safety)

- Solicited local (injection site) reactions and systemic ARs for 7 consecutive days starting from Day 0 to Day 6;
- Unsolicited AEs from Day 0 to Day 28.

5.1.1.2. Co-primary Endpoints (Immunogenicity)

- Geometric mean titers (GMT) of RSV/A-, RSV/B-, hMPV/A-, and hMPV/B-specific NAb at Day 28;
- GMT of RSV and hMPV prefusion F protein-specific IgG antibody titers at Day 28;
- Proportion of subjects with a ≥ 4 -fold increase in serum anti-RSV/A-, RSV/B-, hMPV/A-, and hMPV/B-specific NAb from prevaccination/baseline (Day 0) to Day 28 after vaccination (defined as SRR);
- Proportion of subjects with ≥ 4 -fold increase (SRR) in RSV- and hMPV-specific IgG antibody titers from prevaccination/baseline (Day 0) to Day 28;
- Geometric mean fold rise (GMFR) at Day 28 versus Day 0 in serum anti-RSV/A-, RSV/B-, hMPV/A-, and hMPV/B-specific NAb and RSV and hMPV prefusion F protein-specific IgG antibody titers.

5.1.2. Secondary Endpoints

5.1.2.1. Safety Secondary Endpoints

- SAEs, MAAEs, AESIs (including pIMCs) and AEs leading to trial withdrawal up to Day 365 (end of the main trial);
- Mild, moderate, or severe LRTI caused by RSV and/or hMPV (CESI) up to Day 365;
- Clinical safety laboratory parameters at screening, and Days 0, 7, and 28;
- Mild, moderate, or severe LRTI cases not caused by RSV or hMPV up to Day 365.

5.1.2.2. Immunogenicity Secondary Endpoints

- GMT of RSV/A-, RSV/B-, hMPV/A-, and hMPV/B-specific NAb at Days 0, 180, and 365;
- GMTs of RSV and hMPV prefusion F protein-specific IgG antibody titers at Days 0, 180, and 365;
- Proportion of subjects with a ≥ 4 -fold increase (SRR) in serum anti-RSV/A-, RSV/B-, hMPV/A-, and hMPV/B-specific NAb from prevaccination/baseline (Day 0) to Days 180, and 365 after vaccination;
- Proportion of subjects with an ≥ 8 -fold increase in serum anti-RSV/A-, RSV/B-, hMPV/A-, and hMPV/B-specific NAb from prevaccination/baseline (Day 0) to Days 28, 180, and 365 after vaccination;
- Proportion of subjects with ≥ 4 -fold increase (SRR) in RSV- and hMPV- prefusion F protein-specific IgG antibody titers from prevaccination/baseline (Day 0) to Days 180 and 365 after vaccination;

This document is confidential.

- GMFR at Days 180 and 365 versus Day 0 in serum anti-RSV/A-, RSV/B-, hMPV/A-, and hMPV/B-specific NAb and RSV and hMPV prefusion F protein-specific IgG antibody titers;
- Reverse cumulative distribution (RCD) of serum NAb and IgG antibody titers at Days 0, 28, 180, and 365.

CCI

This document is confidential.

6. Analysis Sets

This section will provide definitions of analysis sets to be analyzed.

6.1. Main Trial Analysis Sets

6.1.1. All Enrolled Set

The All Enrolled Set will include all screened subjects who provide informed consent and provide demographic and/or baseline screening assessments, regardless of the subject's randomization and vaccine group allocation status in the trial. Unless specified otherwise, this set will be used for summaries of subject disposition and listings.

6.1.2. Randomized Set

The Randomized Set will include all enrolled subjects who have been randomized.

6.1.3. Safety Set

The Safety Set will consist of all subjects who received any amount of IVX-A12 or placebo. Subjects will be analyzed as "treated" (i.e., according to the vaccine a subject actually received, rather than the vaccine to which the subject may have been randomized). The set will be used for all analyses of safety endpoints.

6.1.4. Full Analysis Set

The Full Analysis Set (FAS) will include all randomized subjects and received a dose of IVX-A12 or placebo. Subjects will be analyzed according to randomized group. This set will be used for analysis of demographics and other baseline characteristics and subject listings for immunogenicity.

6.1.5. Per Protocol Set

The Per Protocol Sets (PPS) will include all subjects in the FAS who received a dose of IVX-A12 or placebo and have no major protocol deviations, which may exclude subjects from PPS. Subjects will be analyzed according to randomized group. If a subject has a major protocol deviation or RSV/hMPV infection after Day 28, their post-Day 28 data point may be excluded. Blinded data review meeting (BDRM) will be conducted prior to each Interim Analysis and prior to data base lock and unblinding of the vaccine groups. During the BDRMs, a final decision (sponsor call) will be taken as to which subjects/visit will be excluded.

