4.4 Rationale for the Proposed Trial

Elderly adults, especially those with underlying chronic diseases, are highly susceptible to viral causes of community-acquired pneumonia caused by influenza virus, RSV, and hMPV [25; 11; 31; 40]. Although the US FDA recently approved the first two RSV vaccines to prevent RSV disease [41], this proposed trial evaluating IVX-A12 remains relevant for the following reasons: to assess immune responses induced by A12a to hMPV in addition to RSV, and to describe the persistence of those induced immune responses over time. This Phase 2a clinical trial is evaluating the safety and immunogenicity of an unadjuvanted dosage level of 150 µg RSV/150 µg hMPV of IVX-A12 (IVX-A12a) and a dosage level of 150 µg RSV/150 µg hMPV of IVX-A12 adjuvanted with MF59 (IVX-A12d) compared to placebo in adults 60 to 85 years of age. Safety and immunogenicity data from this proposed Phase 2a

clinical trial will allow the selection of an optimal dosage level and formulation of IVX-A12 for adults 60 to 85 years of age in future clinical trials.

The dosage level and formulations of IVX-A12 for this Phase 2a clinical trial have been selected based on the totality of the IVX-A12 nonclinical data and the interim safety and immunogenicity clinical data from the ongoing IVX-A12 Phase 1 clinical trial. Either of the two different IVX-A12 formulations, IVX-A12a and IVX-A12d, or placebo will be administered as a single IM dose to older adult subjects enrolled into two age strata (adults 60 to 69 years of age and elderly adults 70 to 85 years of age). Eligible older adult subjects were randomized to the different trial groups to ensure balance among the groups.

This Phase 2a clinical trial includes a sentinel group of 40 subjects (16 subjects per active treatment group [$n=32$]; 8 subjects in the placebo group) to conservatively assess the 150 μ g RSV/150 μ g hMPV dosage level in combination with MF59.

Subsequently, based on IA from Day 28 of this trial and from emerging data of the IVX-A12 Phase 1 trial (ICVX-12-101), the trial Sponsor has determined that the dosage level and formulation of IVX-A12 to be carried forward for further evaluation will be IVX-A12a [150 μ g RSV/150 μ g hMPV with no adjuvant]. Therefore, to evaluate the persistence of RSV and hMPV antibodies long term follow-up will be offered to the IVX-A12a vaccinees and contemporaneous placebo recipients.

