- 8) Per medical history, subjects with chronic active hepatitis B or hepatitis C infection, human immunodeficiency viruses type 1 or type 2 infection, acute polyneuropathy (such as Guillain-Barré syndrome), or chronic idiopathic demyelinating polyneuropathy; subjects whose hepatitis C antibody test is positive but whose viral loads are negative may be enrolled;
- 9) Acute illness, with or without fever at the time of planned vaccination;
- 10) History of hypersensitivity or serious adverse reactions to vaccines, such as anaphylaxis or angioedema, or any known allergies to any component of the IVX-121 and/or IVX-241 vaccine, or hypersensitivity to latex;
- 11) Abnormal function of the immune system resulting from clinical conditions including chronic administration of systemic corticosteroids (oral/intravenous/IM at a daily dose equivalent of >20 mg prednisone in a period of more than 14 days), or administration of immunosuppressive chemotherapy, biologics, or radiotherapy within the past 3 months prior to planned vaccination;

- 12) Subjects who have received treatment with immunoglobulins or other biologics, such as immunosuppressive therapies expected to modify immune responses to vaccination (including monoclonal antibodies [MAbs] for chronic underlying conditions) within the past 3 months prior to planned vaccination;
- 13) Trial Personnel as an immediate family or household member
- 14) For licensed vaccines:
 - a) Receipt of licensed inactivated vaccines (including seasonal influenza vaccine) within 14 days prior to trial vaccine administration on Day 0, or licensed replicating vaccines such as RNA or live-attenuated virus vaccines within 30 days prior to Day 0.
 - b) Receipt of licensed vaccines is permitted after completion of the Day 28 visit.
 - c) Receipt of any licensed COVID-19 vaccines is permitted if dosing regimen completed within 21 days prior to Day 0 or after completion of the Day 28 visit.

There may be instances when individuals meet all eligibility criteria except one that relates to transient clinical circumstances (e.g., fever or recent use of excluded medication[s] or vaccine[s]). Under these circumstances, eligibility for enrollment may be considered if the appropriate window for delay has passed, inclusion/exclusion criteria have been rechecked, and if the subject is confirmed to be eligible ([Section 7.4](#)).

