6.3. Protocol Deviations

Protocol deviations are defined as instances in which subjects or investigational site study personnel fail to adhere to the protocol requirements (e.g., eligibility criteria, addition or deletion of tests, dosing, duration of treatment, and/or any other aspect of the study design) and the deviation is considered major if the deviation has the potential to impact subject safety or the primary and secondary endpoints of the trial. Deviations are collected in Clinical Trial Management System (CTMS).

This document is confidential.

7. General Aspects for Statistical Analysis

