9.1.2. Secondary Immunogenicity Endpoint(s) and Analyses

The secondary immunogenicity endpoints are defined in [section 5.1.2.2](#). The definition of geometric mean fold rise (GMFR) is provided in [section 7.1](#).

This document is confidential.

The GMTs and adjusted GMTs for serum anti-RSV/A-, RSV/B-, hMPV/A- and hMPV/B-specific NAbs by live-virus assays at Days 180, and 365 will be calculated as described in [section 9.1.1.1](#). The RSV and hMPV prefusion F protein-specific IgG antibody titers by ELISA will also be calculated at Days 180 and 365 as described in [section 9.1.1.1](#). The analyses will be performed for the following:

- By vaccine group;
- By vaccine group and age subgroup analyses category;
- By vaccine group and baseline tertile;
- By vaccine group, baseline tertile and age subgroup analyses category.

GMTs, descriptive statistics, and 95% CIs will be produced for Day 0 for RSV/A-, RSV/B-, hMPV/A-, and hMPV/B- specific NAbs, and RSV and hMPV prefusion F protein-specific IgG antibody titers.

The GMFRs and adjusted GMFRs using ANCOVA (or ANOVA) for serum anti-RSV/A-, RSV/B-, hMPV/A-, and hMPV/B specific NAb ([live-virus assays]) and RSV and hMPV IgG prefusion F protein-specific antibody titers ([ELISAs]) and the ratios at Days 180, and 365 will be analyzed similarly as described in [section 9.1.1.1](#). The analyses will be performed for the following:

- By vaccine group;
- By vaccine group and age subgroup analyses category;
- By vaccine group and baseline tertile;
- By vaccine group, baseline tertile and age subgroup analyses category.

Data displays will also be produced for repeat titer and fold-rise box plots for Days 0, 180, and 365 as described in [section 9.1.1.1](#).

To assess the durability of RSV/A-, RSV/B-, hMPV/A-, and hMPV/B NAbs, and RSV and hMPV IgG prefusion F protein-specific antibody titers, the geometric fold-rise (decay) from Day 28 to Day 180 and Day 28 to Day 365 will be calculated. 95% CIs will be calculated by back transformation of the 95% CI for the mean of the log2 transformed individual fold rise computed using Student's t distribution. Median and quartiles of the fold-rise in antibody titer from Day 28 to Day 180 and Day 28 to Day 365 will also be displayed. The analyses will be performed for the following:

- By vaccine group;
- By vaccine group and age subgroup analyses category;
- By vaccine group and baseline tertile;
- By vaccine group, baseline tertile and age subgroup analyses category.

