To identify unknown RSV or hMPV infections, boxplots will be produced for serum anti-RSV/A-, RSV/B-, hMPV/A- and hMPV/B-specific NAb to display the fold-rise from Day 28 to Day 180, Day 28 to Day 365, and Day 180 to Day 365. The box plots will be produced for the PPS and will utilize log2 transformed fold-rise and back-transformed. Listings will also be generated for serum anti-RSV/A-, RSV/B-, hMPV/A- and hMPV/B-specific NAb, where fold increase ≥ 8 , from Day 28 to Day 180, Day 28 to Day 365, and Day 180 to Day 365. The listings will be produced for the FAS.

CCI

This document is confidential.

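### RSV titers drawn after a permitted licensed RSV vaccine have no pre-specified handling in the secondary Day 180 and Day 365 persistence results

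*SAP*

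**What the plan says.** Protocol 7.2, criterion 14b: "Receipt of licensed vaccines is permitted after completion of the Day 28 visit". No exception is made for RSV vaccines. The separate RSV/hMPV vaccine criterion covers receipt before entry only. The sponsor knew that such vaccines were available, since Protocol 4.4 notes that "the US FDA recently approved the first two RSV vaccines to prevent RSV disease".

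SAP 9.1 runs immunogenicity on the Per Protocol Set. For late visits SAP 6.1.5 states: "If a subject has a major protocol deviation or RSV/hMPV infection after Day 28, their post-Day 28 data point may be excluded". SAP 6.3 defines deviations as "instances in which subjects or investigational site study personnel fail to adhere to the protocol requirements". At the blinded data review meetings, "a final decision (sponsor call) will be taken as to which subjects/visit will be excluded".

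The results concerned are secondary. SAP 5.1.2.2 lists "GMT of RSV/A-, RSV/B-, hMPV/A-, and hMPV/B-specific NAb at Days 0, 180, and 365", with the matching pre-F IgG titers, fold rises and proportions with 4-fold (NAb and IgG) and 8-fold (NAb) increases. For durability, SAP 9.1.2 says "the geometric fold-rise (decay) from Day 28 to Day 180 and Day 28 to Day 365 will be calculated". The same section adds a screen of later rises: "To identify unknown RSV or hMPV infections, boxplots will be produced", together with a listing of NAb rises of 8-fold or more and Tukey outlier listings for Days 180 and 365.

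**The concern.** The SAP accepts that a late titer raised by something other than the trial vaccine may need to be set aside, because it names infection. It does not name the other obvious source of an RSV boost, a licensed RSV vaccine that the protocol allows from Day 28 on. Infection-boosted titers may be removed, while vaccine-boosted titers stay by default.

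What is at stake is how persistence is read. Protocol 4.4 gives description of persistence as one reason why the trial remains relevant after RSV vaccines were approved. SAP 9.2 drops all extension immunogenicity, so Days 180 and 365 are the only persistence evidence the trial will report. A reader could not separate durability of IVX-A12 from a boost by another product.

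**Working it through.** **1. Does either trigger reach the case?** A deviation under SAP 6.3 requires failure to follow the protocol, and permitted receipt is not a failure. Nor is it an infection. SAP 7.3.2 (missing immunogenicity data), 7.5 (analysis windows), 8.1.4 (vaccine history), 9.1.2 and 12 give no rule for these titers. Only the discretionary decision at the review meeting remains.

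**2. The plan's own titer figure.** Inputs from SAP 4.3.1: SD 0.5 log10, groups of 100, 100 and 50, two-sided 0.05, 2-fold difference (log10 2 = 0.301). Power is 98.9% for 100 v 100 and 93.5% for 50 v 100, in line with the stated figure of more than 90%. The same SD is used below as a yardstick; its use for the decay is an assumption.

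**3. Yardsticks.** The 95% CI half-width, as a fold, is 10^(t × SD × root term):
- placebo GMT, n=50: 10^(2.010 × 0.5/√50) = 1.39
- vaccinee GMT, n=100: 10^(1.984 × 0.5/√100) = 1.26
- vaccinee/placebo ratio: 10^(1.976 × 0.5 × √(1/100 + 1/50)) = 1.48

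**4. Inflation of one arm.** If a share f of titers is raised B-fold, the GMT is multiplied by B^f. Neither f nor B is in the documents; f is assumed to be 5-20%.
- Placebo, B = 4 to 8: 4^0.05 = 1.07 up to 8^0.20 = 1.52. Only the upper end exceeds 1.39.
- Vaccinees, B = 2: 2^0.05 = 1.04 up to 2^0.20 = 1.15, inside 1.26. The decay from Day 28 is overstated by the same factor.
- A responder proportion can rise by at most f, that is 5 to 20 percentage points.

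Uptake accumulates, so the share at Day 180 cannot exceed that at Day 365.

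**5. Effect on the vaccine-placebo ratio.** With equal uptake the ratio shrinks by (placebo rise / vaccinee rise)^f.
- Equal rises: 1.00, no effect.
- 8-fold in placebo, none in vaccinees, f = 20%: 8^0.20 = 1.52, against a yardstick of 1.48.
- In between, take a true ratio of 2.0 with both arms boosted to the same level. The vaccinee rise is then half the placebo rise, and the ratio reads 2.0 × 0.5^f = 1.93, 1.87 and 1.74 at 5, 10 and 20% uptake.

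**6. Would the planned displays reveal it?** Partly. The boxplots show the whole distribution of fold rises in NAb, and the Tukey listings cover NAb and pre-F IgG. None is linked to vaccination records, and the stated purpose of the rise screen is to find infections. Take a vaccinee whose titer has halved since Day 28. A 2-fold boost gives 0.5 × 2 = 1.0, no rise from Day 28. An 8-fold boost gives 0.5 × 8 = 4, below the listing threshold. A boost between Days 180 and 365 could appear in the Day 180 to Day 365 boxplot, but without its cause.

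**The case against.** The case for leaving the plan alone is substantial. The trial is descriptive with no formal hypotheses, and keeping all titers whatever vaccines follow is a legitimate choice. The review meeting is blinded, can exclude individual visits, and under Protocol 13.1 also assesses evaluability of subjects and suitability of the methods. Boxplots, rise listings and outlier listings exist, and decay is shown for placebo as well, so a marked late rise there would be noticed. Subjects stay blinded until their Day 365 assessments are done, so uptake driven by known assignment is unlikely. The magnitudes are wholly assumed. The proposed exclusion selects on a post-randomization event.

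All of this stands, and it limits the point to a modest one. It does not supply a stated rule, and it does not let a reader see how far the late RSV results depend on licensed vaccination.

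Two stronger readings are tempting. First, a reader might infer that the gap favors IVX-A12 over placebo. With similar uptake in the two arms and a rise in placebo at least as large as in vaccinees, the ratio stays the same or shrinks; what is flattered is persistence within an arm. Second, because SAP 11.1 runs exploratory efficacy on the same set, a reader might infer that the infection trigger would delete efficacy cases. The documents point the other way. SAP 6.1.5 speaks of a data point and of visits, Protocol 13.1.1 ties the set to immunogenicity results, and SAP 11.1.1 has its own rule for cases and time at risk. At most this merits an editorial note that the infection exclusion concerns titers.

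**Conclusion.** The gap is real and confined to secondary RSV persistence results: Day 180/365 RSV GMT, GMFR and fold-increase proportions, and the decay from Day 28. As written, RSV titers raised by a licensed vaccine remain unless removed by an unscripted sponsor decision. The direction is towards better apparent persistence.

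The size cannot be derived from the documents. Under the assumed 5-20% uptake it stays within sampling error for vaccinees and exceeds it in placebo only at the upper end. These figures further assume that boosting is unrelated to a subject's titer and that the planning SD applies at late visits.

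Primary Day 28 endpoints are untouched, because the permission starts after that visit. hMPV and safety results are also unaffected. This is a cheap improvement, not a threat to the main conclusions, and retaining the titers is not an error if it is stated and its effect shown.

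**What to change.** In SAP 9.1.2, keep the planned results and add one display, by vaccine group only, that excludes RSV titers drawn after receipt of a licensed RSV vaccine. It should cover, at Days 180 and 365:
- GMT, GMFR and the 4-fold proportion for RSV NAb and RSV pre-F IgG;
- the 8-fold proportion for RSV NAb;
- the decay from Day 28 for both assays.

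Retain hMPV titers. Age and tertile repeats are not needed. Check the existing rise and outlier listings against vaccines recorded as concomitant medications.

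First confirm that vaccines given after Day 28 are captured. Protocol 9.1.2 collects vaccines as prior and concomitant medications, but the only time window it states for them is the year before screening, and a later line limits recorded concomitant therapy to prescription medications. SAP 12 mentions an output added after the tables, listings and graphs were completed. If outputs are already complete, label the new display post hoc.

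The cost is one set of late-visit RSV tables and one merge with the medication data. Losing 5-20% of titers widens the n=100 interval from a factor of 1.26 to 10^(1.986 × 0.5/√95) = 1.26 or 10^(1.990 × 0.5/√80) = 1.29, that is 2.7% to 12.2% on the log scale. The display also selects on a post-randomization event. Both drawbacks are visible because the retained-titer results stand beside it.
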